9.2 Pre-study Screening and Baseline

The following will be done prior to performing any study-specific procedures:

Informed Consent Signed: study-related details will be carefully discussed with the patient. The patient will sign an Informed Consent Form approved by the local Ethics Committee.

9.2.1 Visit 1: Screening, (Day -84 to -15)

- Inclusion/Exclusion Criteria
- Demographics
- Medical History
- Concomitant Medications
- Pregnancy Test (serum β-hCG) for women of childbearing potential only
- Physical Therapy Instructions and Subject Exercise Diary given to subject
- Leg Activity Monitor Given to Subject (applicable for US and Japan only)
- Physical Exam
- Vital Signs Including Weight and Height
- Chest X-Ray and ECG
- Hematology
- Serum Chemistry
- Determination of occult malignancy by occult blood in stools (hemoccult test), finding on chest x-ray, carcinoembryonic antigen, prostate-specific antigen (males only), cancer antigen 125 (females only), α-fetoprotein, and β-hCG
- CESD-R Scale Administration (subject must have score of <16)
- Imaging (head MRI) if no head MRI available that was performed within the last 3 months
- Clinical TBI Evaluation (GOS-E and Motricity Index)

9.3 Baseline and Confirmation of Eligibility

9.3.1 Visit 2: Baseline (Day -14 to -1)

The following will be performed at Baseline:

- Eligibility Criteria Review
- Adverse events
- Concomitant medications
- Pregnancy Test (serum or urine β -hCG) for women of childbearing potential only
- Physical Exam
- Subject Exercise Diary Review
- Leg Activity Monitor data download (applicable for US and Japan only)

SanBio, Inc.

- Vital Signs
- Hematology
- Serum Chemistry
- INR and APTT
- HLA typing (molecular) of each subject
- ApoE4 & BDNF Val66Met genotyping of each subject
- Blood draw for Serum anti-HLA Antibodies
- Blood draw for PBMC
- Imaging (head MRI) with Gadolinium
- Exploratory Imaging (pre- and post-contrast T1-weighted, dual echo, FLAIR MRI, Diffusion tensor imaging (DTI) with tractography and Dynamic Susceptibility Contrast (DSC) MRI for perfusion imaging)
- Clinical TBI Evaluations (FMMS; DRS; ARAT; Gait Velocity; NeuroQOL (Upper Extremity Function and Lower Extremity Function)

9.3.2 Eligibility Confirmation/Randomization

Confirmation of eligibility can only occur after performing all assessments and verifying that the patient meets the inclusion and exclusion criteria for the study. Screening eligibility is confirmed at the blinded site, and the surgical safety (i.e. ability to proceed safely with surgery) will be confirmed at the unblinded site prior to surgery.

9.4 Cell Administration or Sham Surgery (Visit 3: Day 1)

Subjects can be admitted to the clinical site on Day -1 and undergo study surgical procedure on Day 1. Prior to any procedures, the patient will be queried on the use of any or changes in medication or adverse events that have occurred since Baseline.

The patient will be randomized prior to surgery via IWRS. The surgical staff, especially the surgeon, should make every effort to remain blinded to the assigned treatment until the start of the surgical procedures. The patient's group allocation will be known by the unblinded laboratory staff so that the appropriate SB623 dose can be prepared for the patient (if randomized to Group 1).

Prior to cell implantation, either a head CT overlaid with the Baseline head MRI or a head MRI alone will be done to determine the exact locations for the implants. Both International Normalized Ratio of Prothrombin Time (INR) and Activated Partial Thromboplastin Time (APTT) shall be performed in the local lab prior to surgery, both results must be normal according to local lab (e.g. INR >1.2 and APTT >38 seconds).

Group 1:

One burr hole will be made in the skull of the patient in a location that will allow ready access adjacent to the focal area of injured brain tissue region. Cells will be implanted using 3 needle tracks with 5 cell deposits for each track at varying depths. Cell implantation will be standardized as to volume (20 μ L/deposit) and rate (10 μ L /min), with spacing between each implant of approximately 5-6 mm.

Group 2:

Subjects will be given procedures similar to Group 1, except will be given a sham surgery (light sedation, stereotactic procedure, partial-thickness skull outer table burr hole, scalp suture, but no penetration of inner table or dura mater).

After cell implantation or sham surgery, the following will be performed:

- Imaging (head CT only)
- Adverse Events
- Concomitant medications

Protocol TBI-01 Version 5, May 17, 2018
9.5 Visit 4: Follow-Up Period (Study Day 2)

The following will be performed:

- Adverse Events
- Concomitant Medications
- Head MRI
- Subjects will be discharged on Day 2 unless complications or local standard medical practice require a longer stay

9.6 Visit 5: Follow-Up Period (Week 1, Study Day 8 ± 1)

The following will be performed:

- Vital Signs
- Hematology
- Serum Chemistry
- Physical Therapy Instruction and Subject Exercise Diary given to Subject
 - Leg Activity Monitor data download (applicable for US and Japan only)
- Blood draw for Serum anti-HLA Antibodies
- Blood draw for PBMC
- Head MRI with Gadolinium (MRI must be read before re-starting any antiplatelet, anticoagulant, or non- steroidal anti-inflammatory agents)
- Adverse Events
- Concomitant Medications

9.7 Visit 6: Follow-Up Period (Week 4, Study Day 28 ± 7)

- Vital Signs
- Hematology
- Serum Chemistry
- Blood draw for Serum anti-HLA Antibodies
- Blood draw for PBMC
- Subject Exercise Diary Review
- Physical Therapy Instructions and Subject Exercise Diary given to subject
- Leg Activity Monitor data download (applicable for US and Japan only)
- Imaging (head MRI) with Gadolinium
- Exploratory Imaging (Pre- and post-contrast T1 weighted, dual echo, FLAIR MRI, Diffusion tensor imaging (DTI) with tractography and Dynamic Susceptibility Contrast (DSC) MRI for perfusion imaging)
- Clinical TBI Evaluations (FMMS; DRS; ARAT; Gait Velocity; NeuroQOL (Upper Extremity Function and Lower Extremity Function)
- Global Rating of Perceived Change: subject and clinician, 7-point Likert scale
- Adverse Events
- Concomitant Medications

9.8 Visit 7: Follow-Up Period (Week 12, Study Day 84 ± 7)

- Vital Signs
- Hematology
- Serum Chemistry
- Blood draw for Serum anti-HLA Antibodies
- Blood draw for PBMC
- Subject Exercise Diary Review
- Physical Therapy Instructions and Subject Exercise Diary given to subject
- Leg Activity Monitor data download (applicable for US and Japan only)
- Clinical TBI Evaluations (FMMS; DRS; ARAT; Gait Velocity; NeuroQOL (Upper Extremity Function and Lower Extremity Function)
- Global Rating of Perceived Change: subject and clinician, 7-point Likert scale
- Adverse Events
- Concomitant Medications

9.9 Visit 8: Follow-Up Period (Week 24, Study Day 168 ± 7)

- Pregnancy test (serum β-hCG) for women of childbearing potential only
- Physical Exam.
- Subject Exercise Diary Review
- Leg Activity Monitor data download (applicable for US and Japan only)
- Vital Signs
- Chest X-ray and ECG
- Hematology
- Serum Chemistry
- INR and APTT
- Blood draw for Serum anti-HLA Antibodies
- Blood draw for PBMC
- Imaging (head MRI)
- Exploratory Imaging (Pre- and post-contrast T1-weighted, dual echo, FLAIR MRI, and Diffusion tensor imaging (DTI) with tractography and Dynamic Susceptibility Contrast (DSC) for perfusion imaging)
- Clinical TBI Evaluations (FMMS; DRS; ARAT; Gait Velocity; NeuroQOL (Upper Extremity Function and Lower Extremity Function)
- Global Rating of Perceived Change: subject and clinician, 7-point Likert scale
- Adverse Events
- Concomitant Medications

9.10 Visit 9: Follow-Up Period (Week 36, Study Day 252 ± 14)

- Vital Signs
- Hematology
- Serum Chemistry
- Leg Activity Monitor data download (applicable for US and Japan only)
- Clinical TBI Evaluations (FMMS; DRS; ARAT; Gait Velocity; NeuroQOL (Upper Extremity Function and Lower Extremity Function)
- Global Rating of Perceived Change: subject and clinician, 7-point Likert scale
- Adverse Events
- Concomitant Medications

9.11 Visit 10: Follow-Up Period (Week 48, Study Day 336 ± 14) and scheduled early withdraw

- Pregnancy test (serum β -hCG) for women of childbearing potential only
- Physical Exam
- Vital Signs
- Chest X-ray and ECG
- Hematology
- Serum Chemistry
- INR and APTT
- Blood draw for Serum anti-HLA Antibodies
- Blood draw for PBMC
- Imaging (head MRI) with Gadolinium
- Exploratory Imaging (Pre- and post-contrast T1-weighted, dual echo, FLAIR MRI, Diffusion tensor imaging (DTI) with tractography and Dynamic Susceptibility Contrast (DSC) for perfusion imaging)
- Leg Activity Monitor data download (applicable for US and Japan only)
- Clinical TBI Evaluations (FMMS; DRS; ARAT; Gait Velocity; NeuroQOL (Upper Extremity Function and Lower Extremity Function)
- Global Rating of Perceived Change: subject and clinician, 7-point Likert scale
- Adverse Events
- Concomitant Medications

10.0 DESCRIPTION OF STUDY TREATMENT

10.1 Study Product Description

SB623 cells are provided as a 1-mL sterile cell suspension, containing $\geq 8 \times 10^6$ cells/mL, cryopreserved in CryoStorTM freezing media.

10.2 Study Product Packaging

Individual 2-mL Nalgene[™] cryovial with screw cap

10.3 Study Product Shipment and Storage

The cryovials containing the frozen cell suspensions are shipped in a dry nitrogen shipper and should be stored in the vapor phase within the shipping container provided by the Sponsor, or in storage equipment maintaining the same temperature as vapor phase liquid nitrogen until transferred at the site to a GMP-compliant liquid nitrogen container or other acceptable storage container approved by the Sponsor.

The Sponsor will arrange for Study Product to be shipped to the clinical site.

10.4 Preparation and Administration

Details for preparation of the cell suspension for administration and for loading the syringe in the Operating Room (OR) will be provided by the Sponsor. Clinical sites will be provided necessary materials for reconstitution of the cells and will be trained by the Sponsor. The cryopreserved cells will be thawed, washed, centrifuged, and re-suspended in Plasma-Lyte A at varying concentrations for administration to the patient within approximately 3 hours of dose release. Prior to administration, a gram stain and a test for endotoxin will be done and a sterility test initiated on the last cell wash to ensure continued sterility. If the endotoxin level is > 5 EU/mL or the gram stain is positive, implantation will not occur. If the sterility test is positive, an investigation will be conducted to determine the source of the contamination by the sponsor. In addition, identification of the patient will be followed closely for adverse events associated with a possible infection and response to antimicrobial therapy, including frequent clinic visits until any infection is cleared.

This Investigational Product may not be used for any purpose other than this clinical study.

10.5 Study Product Accountability Procedures

The Investigator will be responsible for maintaining inventory and accounting for all Study Product received from the Sponsor. After reconciliation has been completed, all unused Study Product vials received by the Investigator will be returned to the Sponsor in a dry nitrogen shipper stored in the vapor phase. Any partially used vials are to be destroyed at the site per institutional standard operating procedure. Unopened vials will be stored in the vapor phase of liquid nitrogen, or in storage equipment maintaining the same temperature as vapor phase liquid nitrogen, or other acceptable storage container approved by the Sponsor until returned to the Sponsor.

11.0 TREATMENT ASSIGNMENT AND BLINDING

This is a double-blind study. The blind will be maintained by strict role definition and procedures described below:

Unblinded personnel:

- Cell preparation staff
- Unblinded study coordinator
- Surgeon and Operating Room staff
- Designated unblinded sponsor & clinical research organization (CRO) personnel
- Data and Safety Monitoring Board (DSMB) members and the supporting statistician and programmer involved in regular review and generation of unblinded safety data

Blinded personnel:

- Assessment site staff
- Designated blinded sponsor & CRO personnel

In order to maintain the blind the following procedures will be implemented:

- 1) Unblinded cell preparation staff will prepare and perform quality check of the cell suspension for each subject. The identity of the treatment will be concealed by the preparation of study product that is identical in packaging, labeling, schedule of administration, administration, and appearance.
- 2) The neurosurgeon and Operating Room (OR) staff will perform the sham surgery procedure using a surgical script that mimics the cell administration procedure as closely as possible (e.g. sequence of steps and overall time taken in the OR).
- 3) Subjects, assessment site staff, persons performing the assessments, blinded sponsor staff, and blinded CRO staff will remain blind to the identity of the treatment from the time of randomization until database lock and unblinding, using the following methods:
 - a. Randomization data are kept strictly confidential until the time of unblinding, and will not be accessible by any of the blinded study personnel in the study, unless subject level emergency unblinding is required as noted in section 11.1 Emergency Unblinding Procedures.
 - b. MRIs will be analyzed by a central reader post-surgery and blinded reports will be sent back to the assessment site staff (excluding the assessment site efficacy assessor) without any accompanying images. Description of the craniotomy skull defect and needle tract from the stereotactic surgical procedure are unblinding by definition and will therefore be excluded from the blinded head MRI reports. If an unscheduled head MRI is to be done, the same process shall be followed as for the scheduled head MRI scans to maintain blinding, unless a local read is necessary for clinical care per the assessment site investigator's discretion. These unblinding events (e.g., local head imaging reading) will be recorded and reported to the Sponsor.
 - c. To further safeguard maintenance of the blind, primary and secondary efficacy assessments are to be completed solely by the efficacy assessors at assessment sites, who will be segregated from other activities at the assessment site and not have access

to any patient study safety information (e.g. adverse events, concomitant medications, head imaging reports, medical charts, etc.,).

d. All sites will be required to document how they will maintain the blind through a Maintenance of the Blind Plan that will require approval and sign off by the Sponsor.

11.1 Emergency Unblinding Procedures

The blinded treatment assignment/dose information is to be broken only in an emergency when knowledge of such treatment may have an impact on further treatment decisions or aid in the emergency treatment of the subject. The Investigator will obtain the treatment assignment for the specified subject by accessing the IWRS. Date and reason for unblinding are to be recorded and reported to the Sponsor immediately.

12.0 CONCOMITANT MEDICATIONS

All concomitant medications including prescription and over-the-counter drugs taken during the 14 days prior to initial screening or used anytime during the study through 1 year post Study Products will be documented. Documentation through Week 48 will include changes from the prior visit, start and stop dates, dose, and reasons for the medication use.

Investigational drugs or devices for any other indication are not allowed during the study.

13.0 TERMINATION, DISCONTINUATION & LOST TO FOLLOW UP

13.1 Study Termination

The protocol may be terminated at any time by the Sponsor in the event of significant Study-Drug-related adverse effects.

13.2 Site Termination

The study site will be closed if there is evidence of fraud, other unethical conduct, or significant non-compliance to the protocol or to Good Clinical Practices (GCPs). Should patient enrollment be unsatisfactory, or data recording be inaccurate and/or incomplete, the Sponsor may terminate the study site and remove all study materials from the study site.

13.3 Patient Discontinuation

Patients will be free to discontinue from the study at any time without giving a reason(s). Patients will be considered discontinued from the study in the event of any of the following reasons:

- Withdrawal of the patient's consent for any reason
- Investigator's discretion due to patient's medical condition

If patient withdrawal occurs during the study period, the Last Evaluation (Visit 10) visit should be performed, if possible, at the time of patient withdrawal or as soon as possible thereafter.

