¹⁵ Clinician ideally includes assessment site efficacy assessor who does not have access to patient study safety information because Global Rating of Perceive Change is a component of secondary endpoint, thereby maintaining the blind of the trial.

¹⁶ At each time point that serum antibody samples are collected, an additional sample for PBMC will also be collected and stored at the central laboratory

¹⁷ Subjects can be admitted to the clinical site on Day -1 and undergo study surgical procedure on Day 1 only after all other procedures for this visit have been completed. Subjects will be discharged on Day 2 unless complications or local standard medical practice require a longer stay.

Protocol TBI-01 Version 5, May 17, 2018

SanBio, Inc. Schedule of Assessments (Continued)

Confidential and Proprietary

Study Period	Follow-Up Period				
Study Visit	9	10 ¹⁸			
Study Day	252 (± 14)	336 (± 14)			
Study Week	36	48			
Study Month	9	12			
Informed Consent					
Demographics					
Inclusion/Exclusion					
Eligibility Criteria Review					
Randomization					
Medical History					
Physical Therapy Instruction and Subject Exercise Diary given to subject					
Subject Exercise Diary Review					
Leg Activity Monitor data download ⁴	X	Х			
Pregnancy Test ^{5,6}		Х			
Physical Exam.		Х			
Vital Signs	X	Х			
Chest X-Ray and ECG		Х			
Hematology	X	Х			
Serum Chemistry	X	Х			
INR and APTT		X			
HLA typing of each subject					
ApoE4 & BDNF Val66Met genotyping					
Occult Malignancy					
CESD-R Scale					
Head CT					
ImagingHead MRI ⁹		X ¹¹			
Imaging – Diffusion Tensor & Dynamic Susceptibility Contrast Imaging ¹²		Х			
Clinical TBI Evaluations	X ¹⁴	X ¹⁴			
Global Rating of Perceived Change (subject and clinician)	X ¹⁵	X ¹⁵			
Serum for anti-HLA Antibodies		Х			
PBMC Sample ¹⁶		Х			
Adverse Events	X	X			
Concomitant Medications	X	Х			
Sham Surgery or Cell Administration ¹⁷					

¹⁸ Patients who have withdrawn from the study must return for Visit 10 assessments.

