13.4 Patients Lost to Follow Up

Patients who cannot be reached after at least three attempts will be categorized as lost to follow up. The attempts to reach the patients must be documented, with at least one of the attempts written and sent to the patient *via* certified or registered mail. Patients lost to follow up will still be included in the analysis of the study. For patients lost to follow up, the Investigator may check public records for survival status at 12 months.

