18.2.2.1 Primary Efficacy Endpoint Analysis

The primary analysis will be a comparison of the mean change from baseline in the Fugl-Meyer Motor Scale score of SB623 treated subjects (pooling all SB623 doses) to sham surgical controls at 24 weeks. A mixed model repeated measures (MMRM) analysis will be performed with terms for treatment, visit, the baseline Fugl-Meyer Motor Scale score, the GOS-E score at screening, and the treatment-by-visit interaction. The Restricted Maximum Likelihood Estimation procedure will be employed using an unstructured covariance matrix. Missing observations will not be imputed.

Protocol TBI-01 Version 5, May 17, 2018

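### After a one-time implant, study discontinuation for medical condition carries no requirement for a Week 24 FMMS, so the primary endpoint can go missing in an outcome-related way

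*Protocol*

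**What the plan says.** The synopsis and Protocol 4.1 describe a single administration. The primary endpoint (Protocol 5.2.1) is change in FMMS at Week 24; FMMS is scheduled at baseline and Weeks 4, 12, 24, 36 and 48 (15.8.2.1).

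Protocol 13.3 states: "Patients will be considered discontinued from the study in the event of any of the following reasons". Two reasons follow: withdrawal of consent, and "Investigator's discretion due to patient's medical condition". No status is defined in which a patient keeps attending scheduled visits after either.

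Three places deal with assessment on leaving:

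- Protocol 13.3: "the Last Evaluation (Visit 10) visit should be performed, if possible, at the time of patient withdrawal or as soon as possible thereafter".
- Footnote 18 to the visit schedule (Protocol 9.1, repeated in SAP Table 1): "Patients who have withdrawn from the study must return for Visit 10 assessments".
- The heading of Protocol 9.11: "Visit 10: Follow-Up Period (Week 48, Study Day 336 ± 14) and scheduled early withdraw". FMMS is among the assessments listed there.

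On loss to follow-up, Protocol 13.4 says "Patients who cannot be reached after at least three attempts will be categorized as lost to follow up". The attempts must be documented, with at least one by certified or registered mail. It adds: "Patients lost to follow up will still be included in the analysis of the study".

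For the primary MMRM, Protocol 18.2.2.1 says "Missing observations will not be imputed". Section 5.3 of the main SAP imputes single missing FMMS items and gives no rule for a wholly missing visit. The only sensitivity analysis described for the primary endpoint (SAP addendum, section 2.0) removes one subject whose baseline was imputed.

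**The concern.** In a trial of continuing treatment, an investigator may need to stop treatment for medical reasons. Here nothing is left to stop once surgery is over, so discontinuation removes only data. Because the trigger is the patient's medical condition, the patients concerned may differ in motor outcome from those who stay.

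The risk may also differ by arm. Group 1 has the dura opened and three needle tracks placed, while the sham procedure stops short of the inner table (Protocol 6.0). Protocol 14.0 names intracranial infection, bleeding and seizures as possible surgical events. If medical discontinuation fell mainly on SB623 and on patients who were declining, the Week 24 comparison would look too favourable.

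The MMRM protects against this only as far as the decline is already visible in recorded scores. A patient who leaves before Week 4 has no scheduled post-baseline score for the model to use. No planned analysis tests departures from missing at random.

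**Working it through.** **The plan's own figures.** Inputs from Protocol 18.6 and SAP 3.4: mean changes 10.0 and 3.0, SD 7.25, two-sided alpha 0.05, 80% power, 3:1 allocation, 8% dropout.

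- Control n = (1.960 + 0.842)² × 7.25² × (1 + 1/3) / 7² = 11.2, rounded up to 12; with 36 on SB623 the total is 48, as stated.
- Exact t-test power is 80.9% at 36/12 and 77.3% at 33/11.
- 48 × 1.08 = 51.84, rounded up to 52, as stated. (48/0.92 = 52.17 would round up to 53; this does not matter here.)

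So the planned arms are 39 and 13, and the dropout allowance is 52 − 48 = 4 patients.

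**Size of a selective loss.** Let k of n patients in an arm leave. Their Week 24 change would have been D points lower than that of the patients who stay, and v points of that shortfall are already visible at their last recorded visit. With slope b of Week 24 on that visit, a likelihood-based analysis recovers b × v of the shortfall, so

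bias in the arm mean = (k/n) × (D − b × v).

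Assumptions, none given in the documents: b = 0.7, one earlier visit (Week 4), k = 3 or 4, D = 10 or 15, all losses in SB623 (n = 39).

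| k | D | none visible (v = 0) | half visible (v = D/2) | all visible (v = D) |
|---|---|---|---|---|
| 3 | 10 | 3/39 × 10 = 0.77 | 3/39 × 6.5 = 0.50 | 3/39 × 3 = 0.23 |
| 3 | 15 | 3/39 × 15 = 1.15 | 3/39 × 9.75 = 0.75 | 3/39 × 4.5 = 0.35 |
| 4 | 10 | 4/39 × 10 = 1.03 | 4/39 × 6.5 = 0.67 | 4/39 × 3 = 0.31 |
| 4 | 15 | 4/39 × 15 = 1.54 | 4/39 × 9.75 = 1.00 | 4/39 × 4.5 = 0.46 |

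A two-visit simulation (4,000 replicates) of the first two columns of results agrees to within 0.01. With one patient lost and the decline fully visible, the bias is 1/39 × 3 = 0.08 to 1/39 × 4.5 = 0.12.

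**Direction.** The same formula with n = 13 applies to sham. One sham patient with D = 10 gives 1/13 × 10 = 0.77 down to 1/13 × 3 = 0.23, now against SB623. If D = 0 there is no bias.

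**Outer bound.** A plain completer comparison ignores earlier visits. Holding the full SB623 mean at 10, the completer mean is (10 − f × m)/(1 − f), where f = k/39 and m is the mean change of those lost. One lost with m = 3 gives a bias of 0.18; four lost with m = −10 give 2.29. In the extreme case of no true effect, where the four lowest SB623 values are the ones lost and no sham value is, two-sided rejection rises from about 5% to about 12%.

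**Precision.** SE = 7.25 × √(1/39 + 1/13) = 2.32; with 11 sham patients it is 2.48, a rise of 7%. Power with 35 and 13 observed is 82.9%. The issue is bias, not power.

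**The case against.** The strongest reply is that the protocol does measure these patients. Section 13.3 itself asks for the Visit 10 evaluation at withdrawal, and Visit 10 includes FMMS. This stands in part: where the visit takes place, there is outcome data on just the patients in question, and the illustration above gives no credit for it. But an exit score at, say, Week 6 is not a Week 24 score, and the SAP does not say whether or where it enters the model. Section 13.3 makes the visit conditional and dates it to withdrawal; footnote 18 makes it mandatory without saying when.

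The arithmetic is also one-sided. It puts every loss in SB623, uses nearly all or all of the planned dropout allowance and omits Week 12. An investigator acting on a medical problem has probably seen some of the decline, which favours the right-hand column of the table. These criticisms are fair, and for that reason the range runs down to about 0.2.

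A reader might infer that 13.4 closes follow-up after three attempts. It does not. It sets a minimum documented effort before an unreachable patient is labelled lost, keeps that patient in the analysis and bars no later attempt. What remains is that the attempts are not tied to visit windows, and inclusion in the analysis cannot supply a missing Week 24 score.

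A reader might also infer that safety data are thinned. Protocol 16.2 and 16.6 require adverse events to be followed to resolution or a stable endpoint, so that is not supported as a general statement.

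**Conclusion.** The point holds as a design gap. After discontinuation for medical condition the protocol does not require a Week 24 FMMS, the exit assessment is inconsistently specified and has no place in the analysis rules, and no sensitivity analysis for informative dropout is described.

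A reader might go further and conclude that Week 24 scores are lost selectively in patients who do badly, or that the SB623 mean is inflated. The documents show neither how many patients left, nor from which arm, nor how they fared. A medical reason may have nothing to do with motor function, and the MMRM uses whatever decline was recorded before exit.

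With 3 of 39 SB623 patients lost after Week 4, a shortfall of 10 to 15 points, slope 0.7 and no sham losses, the estimate would be too favourable by about 0.2 to 1.15 points against the assumed 7. Losses in sham would push it the other way. That is modest, but it affects the primary result and is cheap to prevent.

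**What to change.** - **Protocol 13.3.** State that after surgery a patient stays in follow-up unless consent is withdrawn or the patient dies. A patient whose condition prevents some procedures still has FMMS and adverse event collection at Week 24 and Week 48 where feasible.
- **Protocol 13.3 and footnote 18.** Reconcile the two on whether the exit Visit 10 is required and when it takes place.
- **Protocol 13.4.** Require a documented contact attempt in the Week 24 window and in the Week 48 window before a patient is finally classed as lost.
- **SAP.** Say how an early-withdrawal FMMS is assigned to a visit, and add a sensitivity analysis for informative dropout, for example a delta-adjusted one applied to each arm separately.

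The cost is protocol wording, a little more site contact effort and one extra analysis. No new procedure is added. The change concerns data collection only and leaves clinical management as it is.
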